6. STUDY DESIGN

6.1.Design

Multi-site extension study of the APLICOV-PC clinical study follow-up.

The plitidepsin doses considered in this trial include the three doses specified in the APLICOV-PC study:

- 1.5 mg of plitidepsin administered as a 1.5-hour infusion, once a day for 3 consecutive days (total dose 4.5 mg).
- 2.0 mg of plitidepsin administered as a 1.5-hour infusion, once a day for 3 consecutive days (total dose 6.0 mg).
- 2.5 mg of plitidepsin administered as a 1.5-hour infusion, once a day for 3 consecutive days (total dose 7.5 mg).

6.2.Primary endpoint

Incidence of complications related to COVID-19 infection.

Evaluation of the principal variable:

The following information will be gathered in this study:

- Readmissions to hospitals and causes, from the last visit of the APLICOV-PC study to the end of the extension study.
- Need for oxygen therapy and duration of the same, from last visit of APLICOV-PC study until the end of the extension study.
- Presence of complications (see annex 5) since last visit of APLICOV-PC study until the end of this extension study by the patient.

Also, once the informed consent has been signed, the following tests will be carried out in the following 7 days:

- Barthel Index [26], to assess the patient's degree of autonomy when performing activities of daily living.
- Evaluation of the dyspnea, according to the mMRC scale [27].
- Evaluation of functional capacity (6 minute walk test) [28].
- Physical examination, including weight, height, BSA, pulse oximetry, PAI (estimated annex 8).

- Full analysis, including inflammation markers.
- Chest X-ray, in patients diagnosed with pneumonia upon admission to hospital, which led to their participation in the APLICOV-PC study.
- Evaluation of pulmonary function, including dyspnea evaluation (mMRC and 6 minute walk test) (annexes 7 and 9) SaO₂, PAFI (direct or estimated) (annex 8), spirometry (forced vital capacity, FEV1 and FEV1/CVF) and the diffusion test.
- Electrocardiogram.
- Heart Ultrasound/MUGA, in patients that suffered a relevant cardiac event while participating in the APLICOV-PC study or in those patients for which it was clinically indicated during follow-up.
- Thus, an evaluation was made of both the ultrasound images and the results of the complementary (analytical or functional) tests necessary for interpreting the long-term evolution of the disease, from the start of the patient's participation in APLICOV-PC to the end of this study.

6.3. Secondary outcomes

Not applicable.

7. SCREENING OF PATIENTS

All patients who participated in and received plitidepsin in the APLICOV-PC study are eligible candidates for participating in this extension study. The investigative team will contact the patient to agree a date for the medical visit. The patient will be invited to participate in the study, and be handed the Patient Information Leaflet for the same, along with all additional information related to the study that is necessary for obtaining their informed consent.

7.1. Inclusion criteria

Patient who participated in the APLICOV-PC study, who has been treated with plitidepsin and gives their consent.

7.2. Exclusion criteria

There are no exclusion criteria for this study.

7.3. Randomisation procedures

Not applicable.

7.4. Masking procedures

Not applicable.

8. WITHDRAWAL AND DISCONTINUATION CRITERIA

8.1. Reason for withdrawal

Patients will be excluded or withdrawn from the study for any of the following reasons:

- Withdrawal of consent by the patient.

All cases of a patient's withdrawal from the study must be documented in the Case Report Form.

8.2. Replacement of subjects and reserve subjects

Not applicable. Given the characteristics of the study, those patients who do not agree to participate in the study, or who withdraw their consent, cannot be replaced.

9. INVESTIGATIONAL PRODUCT

9.1. Description of the investigational product

Plitidepsin is licensed in Australia for the treatment of multiple myeloma.

Plitidepsin is currently being investigated in a study to assess the efficacy and safety of the different doses vs a control arm in patients with moderate COVID-19 infection (NEPTUNO). It is a randomized open-label phase III study in adult patients who require hospitalisation and oxygen supplement to treat a moderate COVID-19 infection. The study is designed to evaluate the safety and efficacy of plitidepsin at a low dose (1.5 mg x 3 days) and at a high dose (2.5 mg x 3 days), and it will be compared with the control arm.

Also, plitidepsin was previously studied in the APLICOV-PC COVID-19 study, a proof of concept clinical trial to evaluate the safety of three doses of plitidepsin (1.5 mg, 2.0 mg and 2.5 mg administered over 3 consecutive days), in adult patients hospitalized for COVID-19 [2]. The aim of this study was to determine the safety and toxicological profile, as well as the efficacy, of each dosage level. The results of this clinical trial indicated a positive benefit-risk ratio for the treatment of COVID-19 infection, given the low incidence of adverse events related to the drug of grade ≥ 3 , and the high proportion of discharges from

hospital on days 8 and 15, together with a significant drop in viral load, with no significant differences observed among the three dosage groups.

9.1.1. Description

Plitidepsin is a powder for concentrate for solution for infusion at a concentration of 2 mg/vial.

9.1.2. Packaging

Plitidepsin 2 mg is presented in a Type I clear glass vial with a bromobutyl rubber stopper covered with an aluminium seal. Each vial contains 2 mg of plitidepsin.

The solvent for the reconstitution of macrogolglycerol ricinoleate (polyoxyl 35 castor oil)/absolute ethanol/water for injection, 15%/15%/70% (v/v/v) is supplied in a Type I colourless glass vial. The ampoules have a volume of 4 ml.

9.1.3. Shipping and storage

Plitidepsin should be stored between 2°C and 8°C and the vials should be kept in the outer carton to protect them from light.

The drug in these conditions is stable for 60 months.

9.2.Dosage and administration

The patients included in the extension study received no treatment whatsoever in relation to the study. To participate in the study, the patients must have previously participated in the APLICOV-PC proof of concept study and may have received:

- 1.5 mg of plitidepsin administered as a 1.5-hour infusion, once a day for 3 consecutive days.
- 2.0 mg of plitidepsin administered as a 1.5-hour infusion, once a day for 3 consecutive days.
- 2.5 mg of plitidepsin administered as a 1.5-hour infusion, once a day for 3 consecutive days.

9.3.Duration of treatment

Not applicable.

9.4.Criteria for dosage modification

Not applicable.

9.5.Treatment accounting and compliance

Not applicable.

9.6.Prohibited drugs

Not applicable. Patients who participate in this extension study may be receiving the medicines that their doctors deem necessary.

9.7.Drug interactions

Not applicable, as no medication is administered in this clinical trial.

10. EVALUATION CALENDAR

	Baseline	Up to day +7
Informed consent ¹	X	
Selection criteria ²	X	
PCR COVID-19 ³		X
Medical history review ⁴		X
Vital signs ⁵		X
Physical examination		X
Symptoms/signs/complications of the disease ⁶ (annex 5)		X
Neurological examination		X
Pulmonary function ⁷		X
Barthel scale		X
Electrocardiogram ⁸		X
Haemogram and differential count ⁹		X
Biochemistry ¹⁰		X
Coagulation ¹¹		X
C-reactive protein		X
Chest x-ray ¹²		X
SARS CoV2 IgG Serology		X
Ultrasound / MUGA ¹³		X
Other pharmacological treatments ¹⁴	X	X
Adverse events ¹⁵		X
Hospital readmissions ¹⁶	X	
Need for oxygen therapy ¹⁶	X	
X-rays / complementary tests ¹⁷	X	
1 The patient will sign the informed consent before undergoing any specific study procedure that is not part of normal clinical practice. 2 The patient must meet all the inclusion criteria in order to be included in the study. 3 It will be confirmed via a PCR test that the patient has no COVID infection at the moment of being recruited to the study. 4 The code assigned to the patient for participation in the (APLICOV-PC) reference study will be recorded. It will be confirmed if the patient has presented new COVID-19 episodes since the study ended, and if they have been vaccinated / the type of vaccine / received doses. Details of hospital readmissions and causes and the need for oxygen therapy were collected, from the last visit of the APLICOV-PC study to the signing of the informed consent form, and subsequently to the end of the study. 5 Vital signs: temperature, arterial tension, heart rate, respiratory rate. 6 Presence of complications (see annex 5) since the last visit of the APLICOV-PC study until the end of this extension study. 7 Evaluation of pulmonary function, including dyspnea evaluation (mMRC and 6 minute walk test) (annexes 7 and 9) SaO2, PAFl (direct or estimated) (annex 8), spirometry (forced vital capacity and FEV1) and the diffusion test. 8 The electrocardiogram: overall evaluation and measurement of PR, QT and RR intervals. Save the ECG in the patient's history. 9 Complete blood count, including inflammation markers. 10 It will include creatinine, ions, calcium, albumin, transaminases, bilirubin, alkaline phosphatase, LDH, CK, ferritin and troponin. 11 It will include D-dimer. 12 A chest X-ray will be taken for patients diagnosed with pneumonia upon admission to hospital, which led to their participation in the APLICOV-PC study. 13 A heart ultrasound / MUGA will be performed on patients who suffered a relevant cardiac event during their participation in the APLICOV-PC study. 14 All pharmacological treatments received by the patient since the last visit of the APLICOV-PC study to the signing of the informed consent form, will be collected. 15 Serious and non-serious adverse events related to the study procedures, from the signing of the informed consent until the end of the patient's participation in the study, will be collected. 16 If the patient so requested, their hospital readmissions/oxygen therapy, since the last visit of the APLICOV-PC study to the signing of the informed consent for the extension study, will be collected. 17 Collection of ultrasound images or the results of complementary (analytical or functional) tests necessary for interpreting post COVID-19 evolution.		

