11. ADVERSE EVENTS

No adverse effects were expected in this study, as no adverse events suspected of being related to plitidepsin in the treated patients have been reported since the APLICOV-PC study ended. However, if an adverse effect is observed that may be related to the study procedures, pharmacovigilance will be notified according to the current regulations.

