5.5 Deaths

The number and percentage of patients who died during the study will be provided. Patients who have died due to an AE will be described in more detail, indicating all the variables related to the AEs registered in the electronic case report form (eCRF).

All the analyses will be performed separately for each arm and a total column will be added.

6 Patients description

6.1 Demographic data description. General considerations.

The characteristics of the patients will be described and the unavailable information will be detailed; not available values will not be taken into account in the percentage calculation, only valid percentages will be presented. The analysis will be carried out on the full population and all results will be provided by treatment arm. Aggregated results as well as patient listings will be provided.

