- Number and percentage of patients who have received any COVID-19 vaccine and the number of doses.
- Number and percentage of related or unknown post-COVID-19 complication. Worst per patient.
- Number and percentage of all post-COVID-19 complications. Worst grade per patient.
- Number and percentage of related post-COVID-19 complications. Worst grade per patient.
- Number and percentage of patients with at least AE.
- Number and percentage of patients with at least SAE.
- Number and percentage of patients with at least grade ≥ 3 AE.
- Number and percentage of patients with AEs by system organ classes (SOC) and preferred term (PT), regardless of relationship.
- The maximum, minimum, Q1 and Q3, mean, median and Std of laboratory parameters.
- Aplicov-pc summary of Demographic and Other Baseline Characteristics table of patients include in this study by dose and severity of disease.
 - Median (range) time from symptom onset to first plitidepsin administration, days
 - Number of comorbidities, n (%) (none, one, two or more)
 - Comorbidities, n (%) (Cardiac disease, Kidney disease, Liver disease, Lung disease (COPD), Asthma, Diabetes, Hypertension, Obesity)
 - Clinical status at randomization, n (%)
 - Vital signs, median (range) (Body temperature, $^{\circ}\text{C}$, Systolic blood pressure, mmHg,
 - Diastolic blood pressure, mmHg, Heart rate, bpm, Respiratory rate, bpm, SpO2
 - B, %, On oxygen at baseline, n (%))
 - Laboratory parameters, median (range) (WBC, $\times 10^9/\text{L}$, Platelet count, $\times 10^9/\text{L}$, Lymphocytes, $\times 10^9/\text{L}$, Serum creatinine, $\mu\text{mol}/\text{L}$, ALT \times ULN, AST \times ULN, LDH \times ULN, CPK \times ULN, GGT \times ULN, C-reactive protein, Ferritin, D-dimer)
 - log10 copies/mL viral load, median (range)
 - Days from Plitidepsin to first complication
 - Days from hospital discharge to first complication
 - Time from Plitidipesin first-dose to E-APLICOV inclusion (Month)

9 Listing

- Post-COVID-19 complications will be listed.
- Hospital readmission will be listed
- Oxygen therapy will be listed
- The medication administered before starting the 6MWT will be listed.
- The results of the ECG will be listed.

- The results of the chest X-ray will be listed.
- The ECHO/MUGA results will be listed
- The hematological laboratory parameters will be listed.
- The coagulation laboratory parameters will be listed.
- The biochemistry laboratory parameters will be listed.

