Listing 12.1 Physical examination

Dose cohort	Subject id.	Physical examination	Date	System	Finding

Listing 12.2 Neurological examination

Dose cohort	Subject id.	Neurological examination	Date	Finding

Table 12.3 Electrocardiogram

ECG Continuous endpoints	Dose Cohort																
	1.5						...						Total				
	N	Mean	Median	Range	Q1	...*	N	Mean	Median	Range	Q1
QT (ms)																	
PR (ms)																	
RR (ms)																	

* Q3 and Std.

Table 12.4 COVID-19 (PCR)

COVID-19 (PCR)	Dose Cohort			
	1.5 mg N=X	2.0 mg N=X	2.5 mg N=X	Total N=X
	n (%)			
Has a PCR test been performed?				
Yes				
No				
PCR result				
Positive				
Negative				

Listing 12.3 COVID-19 (PCR)

Dose cohort	Subject id.	PCR test been performed	Date	Result

Table 12.5 COVID-19 (history and IgG serology)

COVID-19	Dose Cohort			
	1.5 mg N=X	2.0 mg N=X	2.5 mg N=X	Total N=X
	n (%)			
Has the patient been diagnosed of COVID-19 since the completion of APLICOV-PC study?				
Yes				
No				
Results IgG				
Positive				
Negative				
Inconclusive				
Has the patient received any COVID-19 vaccine?				
Yes				
No				
Doses received				
1				
2				
3				

Listing 12.4 COVID-19 history

Dose cohort	Subject id.	Diagnosed of COVID-19 since the completion APLICOV-PC study	Diagnosed date	End infection Date	Ongoing

Listing 12.5 COVID-19 Serology SARS-CoV-2

Dose cohort	Subject id.	Serology performed	Date	Result IgG

Listing 12.6 Vaccination schedule

Dose cohort	Subject id.	Vaccination	Dose	Vaccine type	Date

Table 12.6 Pharmacological treatment

Pharmacological treatment	1.5 mg N=X		2.0 mg N=X		2.5 mg N=X		Total N=X	
	N	%	N	%	N	%	N	%
Has the patient received any pharmacological treatment?								
ATC1	ATC2							
	ATC2							
ATC1	ATC2							

Listing 12.7 Pharmacological treatment

Dose cohort	Subject id.	Active ingredients	Start date	End Date	Ong.	Duration	Dose	...(*)

* Units, Frequency, Administration route and Indication.

Table 12.7 Summary of Adverse Events

Patients	1.5 mg N=X		2.0 mg N=X		2.5 mg N=X		Total N=X	
	N	%	N	%	N	%	N	%
Patients with AEs								
Patients with Grade >=3 AEs								
Patients with SAEs								

Table 12.8 Summary of AEs, regardless of relationship, by SOC and PT by dose cohort and overall

MedDRA SOC Preferred Term	Dose Cohort			
	1.5 mg N=X	2.0 mg N=X	2.5 mg N=X	Total N=X
	n (%)			
Subjects with any AE				
Gastrointestinal disorders				
Abdominal pain				
....				
General disorders and administration site conditions				
Asthenia				
Chest discomfort				

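### The protocol collects only procedure-related adverse events, but the SAP labels its adverse event tables as regardless of relationship and never defines that relationship

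*Protocol*

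**What the plan says.** **Collection (protocol).** The evaluation calendar in section 10 has a single row for adverse events. Its footnote 15 defines what is recorded: "Serious and non-serious adverse events related to the study procedures, from the signing of the informed consent until the end" of the patient's participation. Section 11 ties reporting to the same condition: "if an adverse effect is observed that may be related to the study procedures, pharmacovigilance will be notified according to the current regulations". No other part of the protocol provides for recording AEs that are unrelated to a procedure.

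**Reporting (SAP).** Section 8 plans counts of patients with any AE, any serious AE and any grade ≥3 AE, and then "Number and percentage of patients with AEs by system organ classes (SOC) and preferred term (PT), regardless of relationship". The table shells follow: "Table 12.8 Summary of AEs, regardless of relationship, by SOC and PT by dose cohort and overall", and Table 12.9 with the same qualifier by grade. Table 12.7 is a plain summary of AEs, serious AEs and grade ≥3 AEs. Listing 12.8 is titled as covering all adverse events and has a Relationship column. SAP 5.5 adds: "Patients who have died due to an AE will be described in more detail".

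**Setting.** The protocol's section 6.2 says that "once the informed consent has been signed, the following tests will be carried out in the following 7 days". Section 9.7 notes that "no medication is administered in this clinical trial".

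**The concern.** The set of events collected and the set the tables claim to show are different. A title that says regardless of relationship tells the reader that no event was left out because of its attribution. Footnote 15 leaves events out for exactly that reason, and nothing in the SAP warns the reader.

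Tables 12.7 and 12.8 are laid out by plitidepsin dose cohort with a total column, and Table 12.9 is produced for each dose and the total. A low AE percentage in a column headed 1.5, 2.0 or 2.5 mg would look like the frequency of any AE in that cohort after consent. Under footnote 15 it would show only how often the study tests, such as blood sampling, spirometry and the walk test, caused an event.

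The planned checks would not reveal the gap. SAP section 3 calls for reconciliation of serious AEs between the clinical and pharmacovigilance databases. If sites apply footnote 15 to the one and section 11 to the other, an unrelated serious event would be absent from both.

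**Working it through.** The documents give no AE rate or count for this study, so there is no planned figure to reproduce. The check is a comparison of text.

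**Step 1. Each SAP output against the collection rule.**

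| SAP output | Scope it states | Content if footnote 15 is followed |
|---|---|---|
| Section 8, any AE / serious AE / grade ≥3 AE; Table 12.7 | None stated | Procedure-related events only |
| Section 8, SOC/PT bullet; Table 12.8 | Regardless of relationship | Procedure-related events only |
| Table 12.9 | Regardless of relationship, by grade | Procedure-related events only |
| Listing 12.8 | All AEs, with a Relationship column | Procedure-related events only |
| 5.5, detail on deaths due to an AE | Deaths due to an AE | Deaths due to a procedure-related AE only |

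The qualifier appears in the SOC/PT bullet and in Tables 12.8 and 12.9. Table 12.7 and the other three bullets do not carry it; their defect is that they omit the restriction.

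**Step 2. What could relationship mean?** The SAP does not define it for AEs. There are three candidates:

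- *Study procedure.* Footnote 15 then makes the variable constant. The Relationship column carries no information, and the table titles contradict the collection rule directly.
- *Plitidepsin.* Section 11 of the protocol does refer to events suspected of being related to plitidepsin. On this reading the titles do not strictly contradict footnote 15, but the events are still a procedure-related subset and no title says so.
- *Study disease.* This is the meaning Tables 11.1.1 and 11.1.2 give for complications. The consequence is the same as for plitidepsin.

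There is also a fourth possibility: that the eCRF, which is not among the documents, records more than footnote 15 allows. The SAP titles would then be right and the footnote wrong.

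In every case at least one document needs a change, and the definition is missing.

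**Step 3. What is captured elsewhere.** Annex 5 complications, including an open category for others, are recorded from the last APLICOV-PC visit to the end of the extension, with no procedure restriction. Readmissions and oxygen therapy cover the same period (protocol 6.2 and 12.4). SAP section 7 counts laboratory abnormalities of grade 2 or more and ECG abnormalities. Deaths are counted in their own right under SAP 5.5 and in Table 10.3.

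**Step 4. Possible size (assumption only).** Let *q* be the proportion of patients with at least one AE unrelated to a procedure during the window. The documents give no value for *q*. With the maximum *n* = 42 (protocol 12.2), the expected number of patients with such an event is *n* × *q*:

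- q = 2%: 42 × 0.02 = 0.8
- q = 5%: 42 × 0.05 = 2.1
- q = 10%: 42 × 0.10 = 4.2
- q = 20%: 42 × 0.20 = 8.4

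This is an upper guide to the shortfall in the any-AE row, because a patient who also had a procedure-related AE would still be counted there.

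**The case against.** The strongest reply is that this is a matter of wording. The counts would be correct for the events collected. Because AE relationship is undefined, the phrase could refer to plitidepsin or to the disease, and the titles would then be compatible with footnote 15. The Relationship column in Listing 12.8 would serve little purpose if every event were procedure-related by rule, which suggests that sites may record more. No drug is given, the calendar runs only to day +7, the tables sit under other analyses, and the morbidity that matters to the objective is captured by other items.

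Most of this stands, and it limits the size of the point. It does not remove it. The more generous readings replace a direct contradiction with an unstated restriction, or move the error from the SAP to the protocol.

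Two stronger inferences are tempting, and the documents do not support either:

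- *That the tables are all-cause safety tables and are bound to be wrong.* All-cause is not a term the SAP uses for AEs. Table 12.7 does not carry the qualifier at all. What sites actually entered cannot be known without the eCRF.
- *That near-empty tables would be offered as evidence of long-term safety at each dose.* Neither document proposes that use. The sole objective is post-COVID morbidity, and the protocol lists no secondary outcomes. Even a complete record of AEs over a window this short could not establish long-term safety.

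**Conclusion.** The mismatch is real and should be corrected, as a fault of labelling and scope. If footnote 15 is followed, Tables 12.7 to 12.9 and Listing 12.8 hold only procedure-related events and cannot be read as AE incidence regardless of relationship, by dose cohort or overall. The SAP also leaves undefined the variable on which the qualifier depends.

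The consequence is limited to these non-primary outputs. The number of events left out cannot be derived from the documents; the 0.8 to 8.4 patients shown above rest on assumed proportions of 2% to 20%. The primary endpoint is unaffected, because complications are collected under a separate and wider rule.

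The conclusion assumes that sites apply footnote 15 as written. If the eCRF collected all AEs, the correction belongs in the protocol, and the SAP still needs the definition.

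**What to change.** Reconcile the two documents by one of two routes.

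1. **If collection is complete, relabel.** Retitle the four AE bullets in SAP section 8, Tables 12.7 to 12.9 and Listing 12.8 as AEs related to study procedures, from consent to end of participation. Add one sentence to the SAP stating the footnote 15 restriction, and a matching note to SAP 5.5. This looks like the practical route: inclusion was planned to end in December 2021, and the SAP's history of changes is dated 17 Nov 2022. The cost is a few titles and one sentence, with no new data or analysis.
2. **If data can still be collected, widen the rule.** Have footnote 15 and the eCRF record all AEs and serious AEs from consent, with relationship recorded, and keep the SAP titles. The cost is a protocol amendment (section 14.3) and AE recording over a calendar that runs to day +7 per patient. It cannot recover events that were never recorded for patients who have already finished.

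Under either route, define in the SAP what AE relationship is judged against: study procedure, plitidepsin or study disease. If the eCRF already holds unrelated events, correct footnote 15 and leave the titles as they are.
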